#### **7.3.1 Method of implementing the randomisation/allocation sequence**

The study randomization scheme will use simple randomization with a 1:1 allocation ratio using Microsoft Excel with same number of participants in each of Toric IOLs group and non-Toric IOLs group. The consenting patients will be randomly assigned to one of two groups: Toric IOLs with open loop haptic design and standard non-Toric IOLs of similar haptic design.

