#### **Sample size calculation:**

Sample size test calculation was carried out with the G\*Power 3.1 program (Faul *et al.*, 2007) for comparison of the main outcome measure of dynamic balance (between IOL design) using mixed ANOVA (repeated measures, between factor being the type of IOL).

Based on of the result of dynamic balance measurement in a previous study (Mancini *et al.*, 2011), an estimated medium effect size (0.25) will be used. With a power of 85% and level of significance ( $p$ ) set at 0.05 and effect size of 0.25, 55 participants will be required in each group (Standard non-Toric vs Toric IOLs). Assuming a 20% drop out rate, to secure 55 participants in each group, 70 participants will therefore be recruited in each group. For two groups of participants (Toric versus non-Toric), a total of 140 participants will be recruited.

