### **7.3 The randomisation schemes**

The PI will be responsible for recruitment of potential participants from the Cataract clinic at UHP and oversee the consent and eligibility process carried out by the study coordinator. All potential participants will be allocated a unique identification number. The CI, who is independent of the outcome assessments and interventions, will randomize the participants between the intervention and control groups. He will allocate a pseudonymous participant number from 1 to 140. Using simple randomisation with 1:1 allocation ratio through random.org, the 1 to 140 number will be randomly assigned into two groups (Toric IOLs versus non-Toric IOLs). The randomization list will then be passed to the PI, who when recruiting the participants at the pre-surgery clinic can know which type of IOLs (Toric or non-Toric) to prepare for the cataract surgery. At study commencement, each number will be allocated to one of the two groups randomly. This means that subjects are allocated to either arm of the study at the point of recruitment. The randomized list will be held by the PI, who delivers the intervention surgeries. The PI needs to know which lenses are allocated to the patients for surgery purposes but will not participate in the outcome assessment. The study coordinator who is the assessor of the outcome measures will be masked to the allocation of lenses.

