### **7.4 Blinding**

The participants will be masked to the interventions prior to the surgery. They will be told which IOLs they received at the end of their final visit. The CI will conduct the simple randomization for the participants through the random.org and he will be masked to the outcome assessment. The randomized list of participants will be passed to the PI and his ophthalmologist team to prepare the IOLs and deliver the

Vision and balance changes after bilateral implantation of Toric IOLs  
IRAS ID: 286913

cataract correction surgery. So, the PI cannot be masked to the intervention, but he is masked to the outcome assessment.

The outcome assessors for study visits will be masked to the interventions given to the participants. In the post-surgery study visit, the outcome assessors will carry out the dynamic stability reassessment before any visual assessment to ensure they are still masked to the primary outcome measures as the visual assessment will reveal which types of the IOLs the participants received.

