### 10.3.1 Summary of baseline data and flow of patients

[figure not shown]
Randomization	Sample size calculation with the G* Power 3 program N=140	Randomization list generated in MS Excel at the commencement of the study by the Chief investigator: independent of assessment and intervention	Execution- randomization list will be held by the PI (ophthalmologist at REI) so that they know who is allocated into either the intervention or control groups according to the list.
Outcome measures		Trial description	Outcome recorded
Primary outcomes Dynamic stability	1.Eye gazing characteristics	Gazing duration on obstacles during the obstacle negotiation.  Area of interest and corresponding glazing duration during stair walking	
 
Gazing duration and frequency on obstacles and area of interest.
 
Heat map on area of interest from eye tacking device
 
 
all data will be recorded and saved in file name in the format: participant number-obstacle-trial1/2/3-date.

	2.Movement biomechanics	
-participants perform Timed up and go (TU&G) test involving getting up from chair ,then walking over 3m level ground, turning and walking back to sit down on the chair
 
- participants walk over a 3m level ground with obstacles of different contrast colour to background.
 
- accelerometers of head tilting and change in movement of centre of gravity will be recorded during TU&G test and during crossing over obstacles.
	
 
accelerometers data of change in head tilting and centre of gravity will be recorded
 
Duration in seconds of TU&G test
 
 
all data will be recorded and saved in file name in the format: participant number-obstacle-trial1/2/3-date.

Secondary outcomes	1.Refraction and visual acuity	-standardized protocol for routine visual function test	-vision 20/20, sphere cylinder, axis -DVA, NVA -IOL rotation (for Toric IOL group only)
	2.Questionnaire	Short Fall Efficacy Scale International Fear of Falling Questionnaire CAT-PROM 5 Quality of life Questionnaire	

- A CRF form has been prepared for this study

Vision and balance changes after bilateral implantation of Toric IOLs  
IRAS ID: 286913

**Modified CONSORT flow diagram  
for**

**Vision and balance changes using after bilateral  
implantation of Toric versus non-Toric intraocular lenses in  

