#### 10.4 Subgroup analyses

Within the Toric IOLs group, a subgroup of participants presented with post-surgery IOL rotation > 5 degree will be isolated to compare the outcomes. This subgroup of participants is very likely to need

Vision and balance changes after bilateral implantation of Toric IOLs  
IRAS ID: 286913

another adjustment surgery. Their data will inform the impact of IOLs rotation on surgery complications and whether such rotation may be related to degree of astigmatism.

In both the Toric IOLs and non-Toric IOLs group, subgroups of different degree of astigmatism: mild (<1.50), moderate (1.5-3.0) and severe (3.0+) will be differentiated to compare the outcomes to help inform if Toric IOLs offer similar beneficial effect across cataract patients with wide range of astigmatism. This will help to identify which patients should be referred for Toric IOLs and support evidence-based practice.

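### The allocation list is described as simple randomisation and also as equal arms, with two different tools; the stated 70 per arm is not a property of the method named, and balance on astigmatism is left to chance

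*Combined protocol and SAP*

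**What the plan says.** Four places describe the same list.

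- Section 7.3: "Using simple randomisation with 1:1 allocation ratio through random.org, the 1 to 140 number will be randomly assigned into two groups".
- Section 7.3.1: "simple randomization with a 1:1 allocation ratio using Microsoft Excel with same number of participants in each" group.
- Section 7.4: "The CI will conduct the simple randomization for the participants through the random.org".
- Section 10.3.1, table: "Randomization list generated in MS Excel at the commencement of the study by the Chief investigator".

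The sample size text in Section 3.3 depends on equal arms: "to secure 55 participants in each group, 70 participants will therefore be recruited in each group". Section 10.1 repeats the 70 per group. Section 10.4 plans comparisons in both arms across three astigmatism bands, cut at 1.5D and 3.0D, to help identify which patients should be referred for Toric lenses. Nowhere are blocks, strata or minimisation mentioned. Sections 7.3 and 10.3.1 have the principal investigator, who recruits and operates, holding the list; Section 7.5 says the chief investigator holds it.

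**The concern.** Simple randomisation allocates each number independently, so the arm totals are random. A list built to contain equal numbers is restricted randomisation. Section 7.3.1 asks for both in one sentence, and the tool is random.org in two places and Excel in two others. A reader cannot tell which list will be generated and could not reproduce it.

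Two things are at stake. First, the planned 70 recruited and 55 retained per arm do not follow from the method named. Second, corneal astigmatism determines how much a Toric lens can change, and Section 10.4 uses it to inform referral, yet neither version of the method controls its balance between arms. The value is available before allocation, because it is an inclusion criterion checked at screening.

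**Working it through.** **Inputs.** From Sections 3.3, 10.1 and 10.3: effect size f = 0.25, alpha 0.05, power 85%, dropout 20%, 55 per arm needed, 70 per arm and 140 in total recruited, and a within-subject factor with two levels (m = 2). The within-subject correlation is not stated; 0.5 is assumed.

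**1. The plan's own figure.** For the between-group test in a repeated-measures ANOVA, the noncentrality is λ = f²·N·m / (1 + (m − 1)ρ) with 1 and N − 2 degrees of freedom. At N = 110, λ = 0.0625 × 110 × 2 / 1.5 = 9.17 and power is 0.851, so 55 per group is reproduced. For dropout, 55 / 0.8 = 68.75, or 69, which the plan rounds to 70.

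**2. Arm sizes under true simple randomisation**, Binomial(140, 0.5):

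| Event | Probability |
|---|---|
| Exactly 70/70 | 0.067 |
| Arms differ by 10 or more | 0.447 |
| 60/80 or worse | 0.108 |

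The 95% range for one arm is 58 to 82.

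**3. Arm sizes under a fixed 70/70 list without blocks.** The split is exact if all 140 numbers are used. If recruitment stopped at 70, a 30/40 or worse split has probability 0.128 (hypergeometric). If it stopped at 120, the standard deviation of one arm's count is √(120 × 0.25 × 20/139) = 2.1, so a typical difference between the arms is about 4.

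**4. Power cost of unequal arms.** With unequal arms, and d = 2f = 0.5, λ = d²·(n₁n₂/N)·m / (1 + (m − 1)ρ).

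| Completers | Power |
|---|---|
| 55/55 | 0.851 |
| 50/60 | 0.848 |
| 45/65 | 0.839 |

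A 60/80 split keeps (60 × 80)/(70 × 70) = 98% of the efficiency of 70/70.

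**5. Balance within an astigmatism band.** The documents give no band sizes, so the sizes below are assumptions. The entries are the probability of a 60:40 or worse split between arms.

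| Band size (assumed) | Simple | Fixed 70/70, no strata |
|---|---|---|
| 10 | 0.75 | 0.75 |
| 20 | 0.50 | 0.47 |
| 47 | 0.14 | 0.07 |
| 70 | 0.12 | 0.03 |

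More marked splits are less common. In a band of 14, 4/10 or worse has probability 0.18 under simple randomisation and 0.16 under the fixed list. In a band of 20, 6/14 or worse has probability 0.12 and 0.09. Forcing equal totals therefore does little for small bands; stratification is what controls them.

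**The case against.** The strongest reply is that the passages, read together, point to a random split of the numbers 1 to 140 into two sets of 70, loosely labelled simple. That is the most natural joint reading. On it, the 6.7% and 10.8% describe a procedure that would not be used. This stands in part: the label and the tool would still need correcting, and balance would be assured only at the last number.

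A reader might infer that the trial would be underpowered. Under simple randomisation there is an 80% chance that one arm has 68 or fewer, and 68 × 0.8 = 54.4 is below 55. But the other arm then has 72 × 0.8 = 57.6, the total is 112 against the 110 required, and the shortfall is 0.6 of a participant in one arm. The documents do not support a claim of lost power.

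A reader might also infer that the arms would drift apart over the three years of recruitment. An unblocked list creates no systematic time trend between arms. Section 10.2 mentions longer waits, but nothing in the documents shows that outcomes would shift as a result.

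Nor does the method make the astigmatism bands unbalanced; it leaves them to chance. In the overall comparison, chance imbalance adds variance, not bias, and covariate adjustment can deal with much of it. Within a band, a 4/10 split still has 40/49 = 82% of the efficiency of 7/7, and a band of 14 would say little even if evenly split. Stratification is thus an inexpensive improvement, not the repair of a bias.

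**Conclusion.** The contradiction is in the current text and has to be resolved before the list can be generated as described. The stated equal arms are not a property of simple randomisation, which delivers 70/70 about one time in fifteen. The consequence for power is small, about one percentage point for plausible splits, given f = 0.25, two time levels and an assumed correlation of 0.5. The case for change rests on a method that can be reproduced and on astigmatism balance that is secured instead of left to chance. The second matters mainly if the severe band, or another, is small; the documents do not say how large any band will be.

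**What to change.** Replace the descriptions in Sections 7.3, 7.3.1, 7.4 and the 10.3.1 table with one method and one tool:

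- A computer-generated 1:1 list with a recorded seed, in randomly varied permuted blocks, with block sizes not disclosed to the surgical team.
- Stratification by corneal astigmatism at screening, below 3.0D versus 3.0D or above (the upper cut in Section 10.4). Surgery is bilateral, so state which eye defines the stratum, for example the first eye to be operated on.
- The chief investigator holds the list and releases each allocation to the surgical team only after consent and confirmed eligibility. The principal investigator no longer holds the full list in advance; otherwise concealing block sizes achieves nothing. This also settles the difference between Sections 7.3 and 7.5 over who holds it.
- The stratification factor, or continuous baseline corneal astigmatism, enters the primary model.

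Before the strata are fixed, reconcile the Section 6.2 exclusion for predicted bilateral post-operative corneal astigmatism below 1.50D with the mild band in Section 10.4. Depending on how the band is measured, the exclusion may leave it small or empty.

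The cost is rewording in four places, one short script and one model term, with no extra visits or data. The downside is that the stratum must reach the chief investigator before each allocation, a small change from passing over a finished list.

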### **7.4 Blinding**

The participants will be masked to the interventions prior to the surgery. They will be told which IOLs they received at the end of their final visit. The CI will conduct the simple randomization for the participants through the random.org and he will be masked to the outcome assessment. The randomized list of participants will be passed to the PI and his ophthalmologist team to prepare the IOLs and deliver the

Vision and balance changes after bilateral implantation of Toric IOLs  
IRAS ID: 286913

cataract correction surgery. So, the PI cannot be masked to the intervention, but he is masked to the outcome assessment.

The outcome assessors for study visits will be masked to the interventions given to the participants. In the post-surgery study visit, the outcome assessors will carry out the dynamic stability reassessment before any visual assessment to ensure they are still masked to the primary outcome measures as the visual assessment will reveal which types of the IOLs the participants received.

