### **3.5 Secondary endpoints/outcomes**

1. The eye tracking characteristics (gaze duration, area of interest by gaze pattern and its percentage duration gaze time).

Vision and balance changes after bilateral implantation of Toric IOLs  
IRAS ID: 286913

2. IOL rotation by measuring degrees of rotation from intended position and degrees rotation from steepest meridian with digital slit lamp and IOL tilt and decentration using Pentacam4. This will be part of the routine eye assessment for post cataract surgery with Toric IOL.
3. Visual acuity which is also part of routine eye assessment for all post cataract surgery patients.
4. Fear of falling and fall efficacy scale via questionnaire.
5. Cataract specific quality of life questionnaire (CAT-PROM 5)

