## 4. TRIAL DESIGN

The study is a randomized controlled trial comparing the change of dynamic stability, gaze characteristics, visual function, and quality of life measurements between Toric and non-Toric intraocular lens (IOL) groups.

Vision and balance changes after bilateral implantation of Toric IOLs  
IRAS ID: 286913

The study is a double masked, parallel group design. 140 cataract patients with astigmatism  $>1.0D$  at the Royal Eye Infirmary (REI) of Derriford Hospital will be recruited and randomly assigned to either receive Toric IOLs or non-Toric IOLs for bilateral lens replacement surgery. The randomization will be conducted by the CI who is not involved in the surgical intervention nor the outcome measure assessments. The participants will not know which types of IOLs they are receiving and the study coordinator who assesses the outcome measures will be masked to the types of IOLs given to the participants. Study visits will be carried out before surgery, 3-6 months after first and second eye surgery.

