## 5. TRIAL SETTING

This is a multi-centre trial. The screening and recruitment of participants will take place at the cataract clinic at the REI of Derriford Hospital, University Hospitals Plymouth NHS Trust. The intervention of Toric IOLs or non-Toric Monofocal IOLs cataract correction surgery will be carried out by the PI and his ophthalmologist team at the REI. The three study visits for outcome measurements will be carried out by masked assessors who are Allied Health Professionals (Optometrists or Physiotherapists) at the UoP (PAHC building).

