### **7.6 Baseline data**

At each study visit based at the UoP, the participant's full name, DOB, address and contact details will be checked for identification purposes. These details will remain separate from the study data which will be identified using the unique study number allocated to the participants.

The outcome measures will include the following:

- General demographic information such as age, gender, ethnicity, relevant medical history, cataract diagnosis and vision assessment results. This will last about 10 minutes.
- Dynamic stability assessment lasts about 30 minutes. Three motion sensors will be put on the participants' body (neck, lower back and upper leg) and they will be asked to wear a special eye tracking glass (figure 1). After that, the participants will be asked to perform a Timed Up and Go (TUG) test which involves getting up from a chair, walking 3m-distance and return to sit back on the chair. They will also be asked to walk over obstacles on level ground and the last mobility task is walking up and down a standardized staircase. Movement outcomes will be measured using three-dimensional motion analysis

Vision and balance changes after bilateral implantation of Toric IOLs  
IRAS ID: 286913

(ProMove 3D, Inertia Technology, The Netherlands) and eye tracking data will be collected *via* Tobii-pro glasses 2 (Tobii AB, Sweden) (figure 2 and 3). Three trials will be taken to estimate the average and the best recorded time will be taken for the TUG test. As all the participants are active community dwelling elderly without mobility problem, the dynamic stability tasks are no more demanding than their usual daily activities. The PPI also include discussion about the demand of the assessment and all participants agreed the dynamic stability tests only required low level mobility and no concerns were raised.

- Some qualitative data will be collected *via* self-administered questionnaires which takes about 15 minutes. Risk of fall will be assessed with the short Fall Efficacy Scale (FES-short) and Fear of Falling questionnaire. Vision specific quality of life will be assessed with CAT-PROM 5 questionnaire.

- Standard visual function assessment will also be carried out to assess visual acuity and degree of astigmatism and this takes about 20 minutes.

A paper CRF has been prepared for this study to collect data directly relevant to the objectives and outcomes measures detailed in the protocol.

[figure not shown]
[figure not shown]

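### Outcome assessors are called masked without exception, but section 7.4 leaves visual acuity inside the examination that it says reveals the lens

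*Combined protocol and SAP*

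**What the plan says.** The masking claims make no exception for any outcome:

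- Section 4 (Trial Design) calls the study double masked and says that "the study coordinator who assesses the outcome measures will be masked to the types of IOLs given to the participants".
- Section 5 (Trial Setting) says "The three study visits for outcome measurements will be carried out by masked assessors who are Allied Health Professionals", naming optometrists or physiotherapists.
- Section 7.3 repeats that the coordinator, as outcome assessor, does not know the allocation.
- Section 7.4 opens its paragraph on assessors with "The outcome assessors for study visits will be masked to the interventions given to the participants".

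The same paragraph of 7.4 then qualifies this. At post-surgery visits "the outcome assessors will carry out the dynamic stability reassessment before any visual assessment to ensure they are still masked to the primary outcome measures", the reason given being that "the visual assessment will reveal which types of the IOLs the participants received".

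Section 3.5 lists as a secondary endpoint "Visual acuity which is also part of routine eye assessment for all post cataract surgery patients". Section 7.6 places acuity and degree of astigmatism together in one visual function assessment of about 20 minutes. Section 10.3.3 compares unaided and aided distance acuity, in LogMAR, between the lenses. The falls scales and CAT-PROM 5 are described in 7.6 as "self-administered questionnaires which takes about 15 minutes".

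**The concern.** The protocol identifies its own unmasking event and then protects one outcome family from it. Unaided acuity is the most direct test of what a toric lens should change, and a letter-chart score depends on participant effort and on how far the examiner presses for further letters. If the examiner already knows the lens from refraction, slit lamp, Pentacam or the dilated view, that pressing can differ by arm, most plausibly in favour of the toric arm. A reader of the trial report would meanwhile take the acuity comparison as masked, because sections 4, 5 and 7.3 say so.

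For the questionnaires the risk is smaller. If a rotated lens were discussed with a participant before the forms were completed, the participant could infer the arm, since section 2.1 says that repositioning to correct astigmatism is possible only with toric lenses.

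**Working it through.** This is mainly a check of the text, with a short calculation to give scale.

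**Step 1. Which outcomes the 7.4 ordering rule covers.**

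| Outcome | Where collected | Ahead of the visual assessment by rule? |
|---|---|---|
| Dynamic stability (primary) | Mobility tasks (7.6) | Yes (7.4) |
| Eye tracking | Recorded during the same tasks (7.6, Appendix 2) | Yes, through the same rule |
| Falls scales, CAT-PROM 5 | Self-administered (7.6) | Not stated |
| Unaided and aided acuity | Inside the visual function assessment (7.6) | No, it is part of that assessment |
| IOL orientation or rotation | Toric group only (10.3.1, Appendix 2) | No, and doing it discloses the arm |

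**Step 2. Is acuity protected some other way?** No section puts unaided acuity ahead of refraction, slit lamp, Pentacam or dilation, and none assigns it to a separate masked person. Section 2.1 has the chief investigator and a co-investigator, both optometrists, carrying out dilation at study visits. Section 7.3 has the chief investigator generating the allocation, so a person who knows the allocation may take part in the visual block.

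**Step 3. Which visit matters.** Sections 10.3.2 and 10.3.3 compare the groups before surgery and after second-eye surgery, that is, at visit 3. An assessor who carried out the visual assessment at visit 2 has, on the protocol's own statement, already learned the lens type. Reordering tests within visit 3 cannot undo that.

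**Step 4. Scale.** The documents give no acuity SD and no estimate of examiner influence. The plan's only design figure, 55 per group, is for dynamic balance. It is reproduced with f = 0.25, alpha 0.05, two measurements and an assumed correlation of 0.5: lambda = 0.25² × 110 × 2 / 1.5 = 9.17, power 0.851. The present point does not depend on it.

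Assume a difference in encouragement between arms of 1 to 3 letters, at 0.02 LogMAR per letter:

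- 1 × 0.02 = 0.02 LogMAR
- 3 × 0.02 = 0.06 LogMAR

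**Step 5. Can this be turned into a false-positive rate?** Assume also an SD of 0.15 to 0.20 LogMAR. The bias is then 0.02/0.20 = 0.10 SD up to 0.06/0.15 = 0.40 SD. With 55 per arm, SE = sqrt(2/55) = 0.191 SD, and the rate is P(|Z + bias/SE| > 1.96).

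- Single post-operative comparison, or group-by-time term at correlation 0.5: shifts of 0.10/0.191 = 0.52 and 0.40/0.191 = 2.10 give about 8% and 55%.
- Between-lens main effect over two times at correlation 0.5: the bias is halved and the SD of the mean is sqrt(1.5/2) = 0.866. The bias becomes 0.10 × 0.5/0.866 = 0.058 SD and 0.40 × 0.5/0.866 = 0.231 SD, giving about 6% and 23%.

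The same assumed bias gives very different rates depending on the ANOVA term, and 10.3.3 does not say which term is the test.

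**The case against.** The best defence is that 7.4 is open about the unmasking and deliberately protects the primary outcome and, in effect, eye tracking. Section 10.3.1 refers to a standardised protocol for visual function testing and section 7.6 to a prepared case report form. Neither is reproduced, and the order and scoring of acuity may be fixed there. Staffing is also partly divided: section 2.1 and Appendix 1 give eye drops to optometrists and mobility testing to physiotherapists. All of this stands, but none of it shows that whoever reads unaided acuity is masked, and the unqualified claims in sections 4, 5 and 7.3 still conflict with 7.4.

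A reader might infer more than the documents support:

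- **That Appendix 2 shows the eye examination coming before acuity and the questionnaires.** It does not. Its rows also put the eye examination above the mobility tests, which would break the rule in 7.4. The table shows which procedures occur at which visit, not their order.
- **That an unmasked assessor takes the questionnaires.** They are self-administered, and the list in 7.6 places them before visual function. Section 7.4 withholds the lens type from participants until the end of the final visit, and section 2.1 mentions advice only if a rotated lens is found. The gap is only that the 7.6 list is not declared to be a running order.
- **That the false-positive rate for acuity rises to about 55%.** That rests on an assumed bias, an assumed SD and one choice of test. The rationale (section 2) also already treats better unaided vision with toric lenses as established, so the realistic harm is an exaggerated difference, not a spurious one.

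**Conclusion.** The point holds as an internal inconsistency and an unsecured secondary outcome. Assessor masking is claimed for all outcomes, 7.4 contradicts this for anything measured in the visual assessment, and acuity is measured there. The documents do not show that acuity will in fact be read unmasked, or that bias will occur; they show that nothing stated prevents it. Exposure is clearest for unaided acuity and slight for the questionnaires.

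The size is unknown from the documents. Under an assumed 1 to 3 letters, the acuity difference would be exaggerated by 0.02 to 0.06 LogMAR. No error rate should be attached to this. The sample size is unaffected, and within a single visit the primary outcome is protected by the 7.4 rule. Knowledge carried from visit 2 into the visit 3 mobility tests is a separate matter. Because the repair is cheap and acuity bears directly on the lens comparison, the change should be made.

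**What to change.** 1. In 7.4, set the order for post-surgery visits: mobility tasks, questionnaires, unaided distance acuity (scored letter by letter to a fixed stopping rule), and only then refraction, aided acuity, slit lamp, Pentacam and dilation.
2. Have the lens-revealing steps done by a different member of the assessor team already described in section 5. Withhold visit 2 findings from the person who reads unaided acuity at visit 3. That person should not be the chief investigator, who generates the allocation. Where this separation cannot be achieved, report visit 3 acuity as unmasked.
3. State in sections 4, 5, 7.3 and 7.4 that refraction, aided acuity and lens position are not masked outcomes.
4. If the standardised visual function protocol already fixes this order, cite it in 7.4.

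The cost is a few lines of text, scheduling of roles at each visit, and open reporting of some secondary outcomes as unmasked. No new test is needed and the sample size does not change. Reordering alone, without step 2, would not secure masking at the visit that is analysed.
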